#### 5. INTRODUCTION

## 5.1 Background and Rationale

Several candidate genes related to dopamine and noradrenergic neurotransmitter systems are associated with attention deficit hyperactivity disorder (ADHD) severity and subtypes (persistence, comorbidity, functional impairment, and treatment effects), such as *DAT1*, *DRD4*, *MAO-A*, *ADRA2A*, *ADRA2C*, *NET*, and *COMT*. Recently, a large-scale, genome-wide study comparing copy number variations (CNVs) in 3,500 ADHD cases versus approximately 13,000 controls revealed that rare, recurring CNVs impacting specific glutamate receptor metabotropic (GRM) genes (ie, *GRM1*, *GRM5*, *GRM7*, and GRM8) were found in patients with ADHD at significantly higher frequencies compared to healthy controls.

Originally developed by Nippon Shinyaku Co., fasoracetam monohydrate (NFC-1, previously referred to as NS-105) is an important candidate to explore for use in restoring metabotropic glutamate receptors (mGluRs) activity in patients with ADHD exhibiting mGluR hypofunction. It has been shown to improve symptoms of depression and memory/learning in animal models. The drug activity is based on regulating the intracellular adenylyl cyclase-activity stimulated by mGluRs and works by inhibiting the brain gamma-aminobutyric acid B (GABA) receptor stimulus response and enhancing the beta-adrenergic receptor response and the acetylcholine-mediated neurologic system response (1).

Data from animal models, pharmacotherapeutic interventions, and brain and genetic studies in humans implicate glutamatergic system involvement in ADHD pathophysiology. Interventions specifically targeting this system remain to be developed even though a recent, large-scale, genome-wide study revealed that rare, recurring CNVs impacting genes in the glutamatergic network (ie, *GRM1*, *GRM5*, *GRM7*, and *GRM8*) were detected in approximately 10% of the total ADHD cases (2).

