#### 8.2.2 Exclusion Criteria

A subject will be excluded from the study if the subject meets any of the following criteria:

- 1. Subject or parent/legal guardian is in the opinion of the investigator mentally or legally incapacitated, has significant emotional problems at the time of the Screening Visit or during the conduct of the study.
- 2. Subjects with a current or relevant history of comorbid major psychiatric disorders (ie, aside from ADHD), including major depression, bipolar disease, schizophrenia, pervasive development disorder, and intellectual disability.
- 3. Subject is currently taking a prohibited medication and/or is unwilling to wean off current ADHD medication to participate in the study.
- 4. Subject has a history of any illness that in the opinion of the study investigator might confound the results of the study or poses an additional risk to the subject by his or her participation in the study.
- 5. Subject has a history of any clinically significant disease that is not currently clinically stable. Subjects with a history of uncomplicated kidney stones may be enrolled in the study at the discretion of the investigator.
- 6. Subject has a known history or presence of syncope, cardiac conduction problems (eg, clinically significant heart block), exercise-related cardiac events including syncope and pre-syncope, or clinically significant bradycardia.
- 7. Subject has a history of stroke, chronic seizures, or major neurological disorder which, in the opinion of the investigator, would interfere with the subject's ability to participate and/or be evaluated in the study.
- 8. Subject is pregnant or a nursing mother.
- 9. Subject has a history of aversion to blood draws that in the opinion of the investigator or parents would result in compromising the study conduct.
- 10. Subject has a history of physiologic difficulty in venous access that in the opinion of the investigator and parent/legal guardian would compromise study conduct.
- 11. Subject has a history of inability to swallow whole unadulterated capsules, which in the opinion of the investigator or parent/legal guardian would compromise study conduct.
- 12. Subject has a systolic or diastolic blood pressure  $\geq$  the 95th percentile for his or her age.
- 13. Subject consumes any alcoholic beverages on a regular basis (weekly or more often).

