6 GENERAL ISSUES FOR STATISTICAL ANALYSIS

6.1 General Statistical Methodology

Data processing, tabulation of descriptive statistics, calculation of inferential statistics, and graphical representations will be performed using SAS® Software (release 9.3 or higher) for Windows, unless otherwise specified.

Continuous (quantitative) variables will be summarized using descriptive statistics including number of non-missing values, mean, standard deviation (SD), median, minimum, and maximum. Where appropriate, estimates will be presented with 95% confidence intervals (CIs).

Categorical (qualitative) variables will be summarized using the number and proportion of each possible value. In general, the denominator for the percentage calculation will be based upon the total number of subjects in the study population for the treatment group. 95% CIs of proportions may also be presented for selected endpoints where applicable. Zero-count levels of variables will not display a percentage.

The minimum and maximum will be reported with the same degree of precision (i.e., the same number of decimal places) as the raw data. Measures of location (mean and median) will be

SAP FINAL Version 2.0

reported to 1 degree of precision more than the raw data and measures of spread (standard deviation) will be reported to 2 degrees of precision more than the raw data.

All statistical tests will be conducted at the 0.05 significance level using 2-tailed tests, and P-values will be reported. Assessments done on unscheduled visits will not be summarized but will be listed.

Page 12 of 88

In general, baseline and safety tables will be completed for the Safety Population unless otherwise specified. Efficacy tables for primary and secondary endpoints will be presented for the ITT Population. However, analyses of the PP Population may be performed if warranted by the data. These potential PP tables are not present in the table index.

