9.3 Vital Signs

Descriptive summaries of actual (absolute) values and changes from baseline will be presented for systolic and diastolic blood pressure, pulse, respiratory rate, and BMI. These tables will be grouped by treatment group, and by visit.

Additionally, the frequency and percentage of subjects with values of Potential Clinical Importance (PCI) will be summarized in shift tables, by treatment group and overall for each study visit. Criteria for assigning PCI to vital signs are as follows:

SAP FINAL Version 2.0

Criteria for PCI Vital Signs and Change in Body Weight						
Measurement	Lower Criterion	Upper Criterion				
Systolic BP	< 90 mmHg	>120 mmHg				
Diastolic BP	< 50 mmHg	>80 mmHg				
Pulse Rate	≤ 50 bpm	≥ 130 bpm				
Respiration Rate	< 10 breaths/minute	>20 breaths/minute				
Body Weight Change	≥ 7% decrease	≥ 7% increase				

Vital signs and weight/height measurements will also be presented in a subject listing.

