9.4 Electrocardiograms

ECG results will be summarized in three ways, as follows:

- 1. A summary of Central ECG results that presents the number and percent of results that are deemed normal, abnormal, and missing.
- 2. A summary providing N and % of evaluations that are interpreted by each investigative site as Normal, Abnormal NCS, Abnormal CS, and missing.
- 3. Tabulation of ECG results that are of potential clinical importance. Criteria for assigning PCI to ECG results are as follows:

Criteria for PCI categories to ECG Results							
ECG Parameter	Lower Criterion	Upper Criterion					
Heart Rate	≤ 50 bpm	≥ 130 bpm					
PR Interval	None	≥ 180 msec					
QRS Interval	None	≥ 100 msec					
QT Interval	None	≥ 450 msec					
QTcB	None	≥ 450 msec					
QTcF	None	≥ 450 msec					
Change in Heart Rate	≤ 50 bpm	None					
	with decrease > 5 bpm						
Change in QTcB	None	≥ 30 msec					
Change in QTcF	None	≥ 30 msec					

Depending on the incidence of abnormal ECG results, some of these displays might not be needed.

ECG results will also be displayed in a separate subject listing.

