Missing	xx(xx.x%)	xx (xx x%)	xx (xx.x%)	xx (xx x%)	xx (xx x%)	xx (xx x%)	xx (xx.x%)	xx (xx x%)
Low	xx (xx.x%)	xx (xx x%)	xx (xx.x%)	xx (xx x%)	xx (xx x%)	xx (xx x%)	xx (xx.x%)	xx (xx x%)
Normal	xx (xx.x%)	xx (xx x%)	xx (xx.x%)	xx (xx x%)	xx (xx x%)	xx (xx x%)	xx (xx.x%)	xx (xx x%)
High	xx(xx.x%)	xx (xx x%)	xx (xx.x%)	xx (xx x%)	xx (xx x%)	xx (xx x%)	xx (xx.x%)	xx (xx x%)

{Continue for all scheduled postbaseline visits and all analytes. Start a new page for every additional analyte}

Note: Percentages are 100*n/N. A low value is a result less than the lower normal reference range; A high value is a result greater than the normal reference range; A normal value is a result which falls between the low and high normal reference ranges.

Source: Listing 16.2.7.1

^[1] Baseline value is on the column, post-baseline value is on the row.

T:\Medgenics\NFC-1\ADHD-201\...\xxx.sas run on DDMMMYYYY at HH:MM on data extracted on DDMMMYYYY

Table 14.3.3.5

Shifts from Baseline of Clinical Laboratory Data: Hematology by Randomized Treatment Safety Population

{Similar shell as Table 14.3.3.4; Source: Listing 16.2.7.2}

Table 14.3.3.6

Shifts from Baseline of Clinical Laboratory Data: Urinalysis by Randomized Treatment Safety Population

{Similar shell as Table 14.3.3.4; Source: Listing 16.2.7.3}

Table 14.3.4.1
Summary of Vital Signs by Randomized Treatment by Study Visit
Safety Population

{Similar shell as Table 14.3.3.1; Source: Listing 16.2.8}

Protocol: MDGN-NFC1-ADHD-201

Page 1 of x Final

Table 14.3.4.2 Potentially Clinically Important Vital Signs by Randomized Treatment Safety Population

Parameter		
Visit	NFC-1	Placebo
Category	(N=xx)	(N=xx)
Temperature (°F)		
Baseline		
n	XX	XX
< 96 °F	xx (xx x%)	xx (xx x%)
\geq 96 °F and \leq 102°F	xx (xx x%)	xx (xx x%)
> 102°F	xx(xxx%)	xx (xx x%)
Missing	xx (xx x%)	xx (xx x%)
Visit 3		
n	XX	XX
< 96 °F	xx (xx x%)	xx (xx x%)
\geq 96 °F and \leq 102°F	xx (xx x%)	xx (xx x%)
> 102°F	xx (xx x%)	xx (xx x%)
Missing	xx (xx x%)	xx (xx x%)

{Continue for all scheduled post-baseline visits and all parameters. Start a new page for every additional parameter, individual parameter ranges are given within the SAP text Section 9.3}

Source: Listing 16.2.8

Page 1 of x Final

Table 14.3.5.1
Incidence of Abnormal ECG Findings: based on Site Interpretations by Randomized Treatment by Study Visit
Safety Population

Visit	NFC-1	Placebo
Category	(N=xx)	(N=xx)
Baseline		
n	XX	XX
Normal	xx (xx x%)	xx (xx.x%)

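### SAP 9.3 promises shift tables with an overall summary for vital signs of potential clinical importance, but shell 14.3.4.2 is not a shift table and cannot show how many subjects became abnormal on treatment

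*SAP*

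**What the plan says.** SAP 9.3 (Vital Signs) fixes limits for systolic and diastolic pressure, pulse and respiration, plus a 7% change in body weight. On how counts and percentages are to be reported, it states that "values of Potential Clinical Importance (PCI) will be summarized in shift tables, by treatment group and overall for each study visit".

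The output that implements this is in SAP Appendix A: "Table 14.3.4.2 Potentially Clinically Important Vital Signs by Randomized Treatment Safety Population". As drawn, it has two columns, NFC-1 and Placebo. Each visit, starting with Baseline, has its own block of n, below, within, above and Missing. The worked parameter is temperature in °F. For the rest, a programming note says that "individual parameter ranges are given within the SAP text Section 9.3".

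On entry, protocol 8.2.2, criterion 12, reads "Subject has a systolic or diastolic blood pressure" and sets the limit at or above the 95th percentile for age. The PCI upper limits in SAP 9.3 are above 120 mmHg systolic and above 80 mmHg diastolic, the same for every age.

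**The concern.** A shift table follows each subject from a Baseline category to a later category. Stacked counts by visit do not: they show how many subjects are outside the limits at each time, but not whether they are the same subjects. Where subjects can enter the trial already outside the limits, the safety question is how many moved from inside to outside on treatment, and the planned table cannot answer it.

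Table 14.3.4.2 is the only planned table that counts subjects outside the blood pressure, pulse and respiration limits of 9.3. The trial has no data safety monitoring board (protocol 12), so the final tables carry much of the group-level safety picture. If programming follows the shell, the study report will not contain the display that the SAP text promises.

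**Working it through.** The plan states no figure for PCI, so there is none to reproduce. The check compares text with shell, then asks what the shell's counts can and cannot determine.

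**1. Text against shell**

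| Feature | SAP 9.3 text | Shell 14.3.4.2 |
|---|---|---|
| Structure | Shift tables | Separate block per visit, Baseline not crossed with later visits |
| Columns | By treatment group and overall | NFC-1 and Placebo only |
| Parameters | Systolic, diastolic, pulse, respiration, weight change | Temperature shown; the rest by reference to 9.3 |

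Temperature is not among the vital signs in protocol 10.3.3.2.1 (heart rate, respiratory rate, systolic and diastolic pressure), nor in the 9.3 criteria. That suggests a template not yet fitted to this trial. The SAP already contains the right layout: laboratory shell 14.3.3.4 puts the Baseline category in the columns and the post-baseline category in the rows.

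**2. Can a subject be PCI before the first dose?**

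Yes, as far as the criteria go. The blood pressure exclusion is a percentile for age and acts only on the high side. The PCI limits are flat values, and the low limits (below 90 systolic, below 50 diastolic) have no numerical counterpart at entry. The documents do not give the percentiles in mmHg or any baseline blood pressure distribution, so the number who would start outside is unknown.

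**3. What the shell's counts determine**

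Inputs: N = 45 per arm (protocol 7.1, approximate). Let b be the number outside at Baseline and v the number outside at a visit. For simplicity, all 45 have both values. The values of b and v are assumed, for illustration only.

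If p subjects are outside at both times, the number newly outside is e = v − p. The shell prints b and v but not p. Since p lies between max(0, b + v − N) and min(b, v):

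- smallest e = max(0, v − b)
- largest e = min(v, N − b)
- number at risk of becoming new cases = N − b

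For b = v = 9: smallest e = max(0, 0) = 0, largest e = min(9, 36) = 9, at risk = 45 − 9 = 36.

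| b = v | Printed at both times | Newly outside, lowest | Newly outside, highest |
|---|---|---|---|
| 5 | 5/45 = 11.1% | 0/40 = 0% | 5/40 = 12.5% |
| 9 | 9/45 = 20.0% | 0/36 = 0% | 9/36 = 25.0% |
| 14 | 14/45 = 31.1% | 0/31 = 0% | 14/31 = 45.2% |

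Two arms could print identical rows of 20.0% and 20.0%, one with no new cases and the other with a quarter of its at-risk subjects newly outside. This follows from the layout alone and needs no assumption about the blood pressure distribution.

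**The case against.** **The text already states the right display.** Appendix A describes its shells as programming guidance that may be updated without amending the SAP. This stands. It makes the point an inconsistency that is cheap to correct, not a wrong rule. But the shell is what programmers build from, so the correction has to be made there.

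**Nothing is lost at subject level.** Listing 16.2.8 shows each subject's values by visit with flags. True, but a reader would have to build the shift count by hand from the listing.

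**Randomisation balances abnormality at entry.** In expectation it does, so the between-arm comparison at a visit is not biased by it. What is missing is the number of new cases in each arm.

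**Change from Baseline is promised elsewhere.** SAP 9.3 does promise descriptive changes, but means and spreads do not count subjects who cross a limit. Shell 14.3.4.1 also borrows the layout of 14.3.3.1, which as drawn has no change column.

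Three stronger readings are tempting, and the documents do not support them.

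- *That the ECG table has the same contradiction.* SAP 9.4 promises only a tabulation of PCI results, and shell 14.3.5.3 matches that. Section 9.4 also already contains criteria for change in QTc.
- *That dropout makes the arm losing more subjects look safer.* SAP 6.1 says that "the denominator for the percentage calculation will be based upon the total number of subjects in the study population for the treatment group", but only as a general rule, and this shell has no percentage footnote. The shell prints n and Missing at every visit, so dilution is visible and can be undone. The last visit is Visit 8/ET, where vital signs are taken. Protocol 8.3 asks for end-of-study evaluations at discontinuation where possible, and 9.9 requires the ET assessments for subjects who stop because of intolerability.
- *That omitting a criterion for a rise in heart rate is an error.* The 9.4 change criterion covers only a low rate "with decrease > 5 bpm", and protocol 5.1 describes the drug as "enhancing the beta-adrenergic receptor response". That is background on mechanism. The documents report no heart-rate finding, and both 9.3 and 9.4 set an upper limit of 130 bpm. A criterion for an increase would be a preference.

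**Conclusion.** The point holds for vital signs. Shell 14.3.4.2 does not deliver the shift tables or the overall summary promised in SAP 9.3, and its worked parameter does not belong to this trial. With the limits and entry criteria as written, the shell cannot distinguish subjects already outside the limits at Baseline from new cases on treatment.

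The size of the ambiguity depends on how many start outside. In the illustration with 9 of 45 at both times, the proportion newly outside could be anywhere from 0% to 25%. The assumptions are about 45 per arm, complete values and invented counts. A reader might want to go further and state what share of flagged subjects were flagged at entry. The documents give no blood pressure mean, SD or within-subject correlation, and no mmHg value for the entry percentile, so no such share can be given.

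The point does not reach body weight, whose criterion is already a change from Baseline. It does not touch the efficacy analysis.

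**What to change.** Keep the 9.3 cut-offs and change the shell before unblinding:

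1. Rebuild 14.3.4.2 on the layout of 14.3.3.4, with Baseline category against post-baseline category at each visit, for systolic pressure, diastolic pressure, pulse and respiration. Leave body weight change as a simple count.
2. Replace the temperature example with a 9.3 parameter.
3. Add the Overall column.
4. For each of the four shifted parameters, add a treatment-emergent row: not PCI at Baseline and PCI at any on-treatment visit, including ET. Its denominator is subjects not PCI at Baseline who have a post-baseline value. State this in a footnote, because it departs from the general rule in SAP 6.1.

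The cost is shell and footnote wording, some programming and a slightly longer table. No new data are needed. Steps 1 to 3 only bring the shell into line with the SAP text. Step 4 also needs a sentence in SAP 9.3 to define the row.

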9.4 Electrocardiograms

ECG results will be summarized in three ways, as follows:

- 1. A summary of Central ECG results that presents the number and percent of results that are deemed normal, abnormal, and missing.
- 2. A summary providing N and % of evaluations that are interpreted by each investigative site as Normal, Abnormal NCS, Abnormal CS, and missing.
- 3. Tabulation of ECG results that are of potential clinical importance. Criteria for assigning PCI to ECG results are as follows:

Criteria for PCI categories to ECG Results							
ECG Parameter	Lower Criterion	Upper Criterion					
Heart Rate	≤ 50 bpm	≥ 130 bpm					
PR Interval	None	≥ 180 msec					
QRS Interval	None	≥ 100 msec					
QT Interval	None	≥ 450 msec					
QTcB	None	≥ 450 msec					
QTcF	None	≥ 450 msec					
Change in Heart Rate	≤ 50 bpm	None					
	with decrease > 5 bpm						
Change in QTcB	None	≥ 30 msec					
Change in QTcF	None	≥ 30 msec					

Depending on the incidence of abnormal ECG results, some of these displays might not be needed.

ECG results will also be displayed in a separate subject listing.

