# 13.1.3 Safety Endpoints

Adverse events will be coded using the most recent version of the Medical Dictionary for Regulatory Affairs (MedDRA) and tabulated by system organ class and preferred term. Adverse events will be analyzed by frequency, severity, relationship to IP, and their effect on participation in the study.

Clinical laboratory values will be compared to normal ranges and flagged for levels of clinical concern. The analysis will focus on the frequencies of abnormal values as well as within-subject changes observed during the course of the study.

Vital signs and ECG recordings will also be examined for changes during the study that may be attributed to exposure to IP.

The C-SSRS will also be examined for changes that may be attributed to exposure to IP.

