# 13.4.4.3 Vital Signs and Electrocardiograms

Vital signs (systolic and diastolic blood pressure, pulse, and respiratory rate), and ECG results will be summarized by visit and treatment group using appropriate descriptive statistics. The number and percentage of subjects with abnormal ECG findings will be summarized by treatment group for each study visit.

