Abnormal – Not Clinically Significant	xx (xx x%)	xx (xx.x%)
Abnormal – Clinically Significant	xx (xx x%)	xx (xx.x%)
Unable To Be Evaluated	xx(xxx%)	xx (xx.x%)
Visit 3		
n	XX	XX
Normal	xx (xx x%)	xx (xx.x%)
Abnormal – Not Clinically Significant	xx (xx x%)	xx (xx.x%)
Abnormal – Clinically Significant	xx (xx x%)	xx (xx.x%)
Unable To Be Evaluated	xx(xxx%)	xx (xx.x%)
Visit 4		
n	XX	XX
Normal	xx (xx x%)	xx (xx.x%)
Abnormal – Not Clinically Significant	xx (xx x%)	xx (xx.x%)
Abnormal – Clinically Significant	xx (xx x%)	xx (xx.x%)
Unable To Be Evaluated	xx (xx x%)	xx (xx.x%)

Note: Percentages are 100*n/N. ECG = Electrocardiogram.

Source: Listing 16.2.9

Page 1 of x

Final

Medgenics, Inc.

Protocol: MDGN-NFC1-ADHD-201

Table 14.3.5.2
Incidence of Abnormal ECG Findings: based on Central Reading by Randomized Treatment by Study Visit
Safety Population

Visit	NFC-1	Placebo
Category	(N=xx)	(N=xx)
Baseline		
n	XX	XX
Normal	xx(xxx%)	xx (xx.x%)
Abnormal	xx(xxx%)	xx (xx.x%)
Unable To Be Evaluated	xx (xx x%)	xx (xx.x%)
Visit 3		
n	XX	XX
Normal	xx (xx x%)	xx (xx.x%)
Abnormal	xx (xx x%)	xx (xx.x%)
Unable To Be Evaluated	xx (xx x%)	xx (xx.x%)
Visit 4		
n	XX	XX
Normal	xx (xx x%)	xx (xx.x%)
Abnormal	xx (xx x%)	xx (xx.x%)
Unable To Be Evaluated	xx (xx x%)	xx (xx.x%)

Note: Percentages are 100*n/N. ECG = Electrocardiogram.

Source: Listing 16.2.10

T:\Medgenics\NFC-1\ADHD-201\...\xxx.sas run on DDMMMYYYY at HH:MM on data extracted on DDMMMYYYY

CONFIDENTIAL AD-ST-33.03 16 Mar 2012

Protocol: MDGN-NFC1-ADHD-201

Page 1 of x Final

Table 14.3.5.3
Potentially Clinically Important ECG Results by Randomized Treatment
Safety Population

Parameter		
Visit	NFC-1	Placebo
Category	(N=xx)	(N=xx)
Heart Rate		
Baseline		
n	XX	XX
≤ 50 bpm	xx (xx x%)	xx (xx x%)
> 50 bpm and < 130 bpm	xx (xx x%)	xx (xx x%)
≥ 130 bpm	xx (xx x%)	xx (xx x%)
Unable To Be Evaluated	xx (xx x%)	xx (xx x%)
Visit 3		
n	XX	XX
≤ 50 bpm	xx (xx x%)	xx (xx x%)
> 50 bpm and < 130 bpm	xx (xx x%)	xx (xx x%)
≥ 130 bpm	xx (xx x%)	xx (xx x%)
Unable To Be Evaluated	xx (xx x%)	xx (xx x%)

{Continue for all scheduled post-baseline visits and all parameters. Start a new page for every additional parameter, individual parameter ranges are given within the SAP text Section 9.4}

Source: Listing 16.2.9

Protocol: MDGN-NFC1-ADHD-201

Page 1 of x Final

Table 14.3.6 Summary of C-SSRS Assessments by Randomized Treatment Safety Population

	NFC-1	Placebo	Overall
Category [1]	(N=xx)	(N=xx)	(N=xx)

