		Visit 8/ET	DDMMMYYYY	XX.XX	XXX	XXX	

{Repeat for all scheduled analytes}

^[1] H = High, L = Low, P = Potential Clinical Importance.

T:\Medgenics\NFC-1\ADHD-201\...\xxx.sas run on DDMMMYYYY at HH:MM on data extracted on DDMMMYYYY

Listing 16.2.7.2 Clinical Laboratory Data: Hematology Safety Population

{Similar shell as Listing 16.2.7.1}

Listing 16.2.7.3 Clinical Laboratory Data: Urinalysis Safety Population

{Similar shell as Listing 16.2.7.1}

Listing 16.2.7.4 Pregnancy Tests Safety Population

{Similar shell as Listing 16.2.7.1, limit to only female subjects, remove flag column}

Listing 16.2.7.5 Urine Drug Screen Safety Population

{Similar shell as Listing 16.2.7.1, remove reference limit columns and flag column}

Protocol: MDGN-NFC1-ADHD-201

Page 1 of x Final

Listing 16.2.8 Vital Signs Safety Population

Treatment: XXXXXX

Subject ID	Visit	Vital Signs Collected?	Date of Measurement	Height (cm)	Weight (kg)	Heart Rate (beats/min)	Respiratory Rate (breaths/min)	Systolic Blood Pressure (mmHg)	Diastolic Blood Pressure (mmHg)	BMI (kg/m^2)
xxxxxxxx	Screening	Yes	DDMMYYYY	XX X	XX.X	XXX	XXX	XX	XX	XX X
λλλλλλλ	Baseline	Yes	DDMMYYYY	XX X	XX.X	XXX	XXX	XX	XX	XX X
	Visit 3	Yes	DDMMYYYY	XX X	XX X*	XXX	XXX	XX	XX	XX X
	Visit 4	Yes	DDMMYYYY	XX X	XX.X	XXX	XXX	XX	XX	XX X
	Visit 5	Yes	DDMMYYYY	XX.X	XX.X	XXX	XXX^	XX	XX	XX X
	Visit 6	Yes	DDMMYYYY	XX X	XX.X	XXX	XXX	XX	XX*	XX X
	Visit 7	Yes	DDMMYYYY	XX X	XX.X	XXX	XXX	XX	XX	XX X
	Visit 8/ET	Yes	DDMMYYYY	XX X	XX.X	XXX	XXX	XX	XX	xx x^
xxxxxxx	Screening	Yes	DDMMYYYY	XX X	xx.x	xxx*#	XXX	XX	XX	XX X
	Baseline	Yes	DDMMYYYY	XX X	xx x^#	XXX	XXX	XX	XX	XX X
	Visit 3	Yes	DDMMYYYY	XX X	XX.X	XXX	XXX	XX	XX	XX X
	Visit 4	Yes	DDMMYYYY	XX X	XX.X	XXX	xxx*	XX	XX	XX X
	Visit 5	Yes	DDMMYYYY	XX X	XX.X	XXX	XXX	XX	XX	XX X
	Visit 6	Yes	DDMMYYYY	XX X	XX.X	XXX	XXX	XX	XX	xx x^
	Visit 7	Yes	DDMMYYYY	XX X	XX.X	xxx*	XXX	XX	XX	XX X
	Visit 8/ET	Yes	DDMMYYYY	XX X	XX.X	XXX	XXX	XX	XX	XX X

Note: * = High, ^ = Low, # = Potential Clinical Significance.

T:\Medgenics\NFC-1\ADHD-201\...\xxx.sas run on DDMMMYYYY at HH:MM on data extracted on DDMMMYYYY

Protocol: MDGN-NFC1-ADHD-201

Page 1 of x Final

Listing 16.2.9 Electrocardiograms (ECGs), Site Interpretation Safety Population

Treatment: XXXXXX

Subject ID	Visit	ECG Collected?	Datetime of Measurement	Investigator Interpretation
xxxxxxxx	Screening	Yes	DDMMYYYY:HH:MM	Normal
	Baseline	Yes	DDMMYYYY:HH:MM	Normal
	Visit 3	Yes	DDMMYYYY:HH:MM	Normal
	Visit 4	Yes	DDMMYYYY:HH:MM	Abnormal – Not clinically significant

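### The SAP summarises ECGs only as normal/abnormal and threshold counts, so a moderate mean shift in QTc, or in PR, QRS or QT, would be poorly shown

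*SAP*

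**What the plan says.** Protocol 13.1.3 sets the aim for these data: "Vital signs and ECG recordings will also be examined for changes during the study that may be attributed to exposure to IP". Protocol 13.4.4.3 gives the method, "ECG results will be summarized by visit and treatment group using appropriate descriptive statistics", and a separate sentence then asks for the number and percentage of subjects with abnormal ECG findings at each visit. Under the schedule of events (Protocol 17.1) a 12-lead ECG is recorded at Screening, at Baseline and at each of Visits 3 to 8/ET.

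SAP 9.4 opens with "ECG results will be summarized in three ways, as follows" and names:

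1. central readings as normal, abnormal or missing;
2. site interpretations as normal, abnormal not clinically significant, abnormal clinically significant, or missing;
3. a "Tabulation of ECG results that are of potential clinical importance". It uses cut-offs for heart rate, PR, QRS, QT, QTcB and QTcF, and for change in QTcB and QTcF (30 msec or more).

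The section then adds: "Depending on the incidence of abnormal ECG results, some of these displays might not be needed".

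Shells 14.3.5.1 to 14.3.5.3 follow this text, with categories by visit and arm and no mean, SD or change. Shell 14.3.5.3, the PCI table, carries the line "Source: Listing 16.2.9". The shell for that listing holds subject, visit, whether an ECG was collected, its date and time, and a column headed "Investigator Interpretation". Listing 16.2.10, the central reading, is specified as a similar shell.

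**The concern.** Counts beyond fixed limits use little of the information in a continuous measurement. A drug that moves QTc by a moderate amount in most subjects takes few of them across a 30 msec change or a 450 msec limit. A by-visit table of value and change would show such a movement directly, from recordings made at Baseline and six treatment visits. Without it, the aim in Protocol 13.1.3 of examining ECGs for changes attributable to the product is only partly met.

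There is also a traceability gap. Table 14.3.5.3 counts numeric results but cites a listing whose shell has no numeric result, so the counts could not be checked against the values behind them.

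**Working it through.** **Document comparison**

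| Safety data | SAP text | By-visit value and change from baseline? |
|---|---|---|
| Laboratory tests | 9.2 | Yes, by arm |
| Vital signs, including pulse | 9.3 | Yes, by arm |
| ECG PR, QRS, QT, QTc | 9.4 | No; categories only |

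Protocol 13.4.4.3 puts ECG results in the same sentence as vital signs for descriptive statistics, then deals with abnormal counts in a second sentence. If counts were all that was meant for ECG, the first sentence would add little. SAP Section 10 records the ECG PCI analysis as an addition and mentions no removal of descriptive statistics.

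**Illustration of size**

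The plan states no ECG figure to reproduce. Inputs:

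- 45 subjects per arm (Protocol 7.1);
- the 30 msec change limit (SAP 9.4);
- assumed, because the documents give neither: SD of within-subject QTc change σ = 12, 15 or 18 ms, and a true mean shift of 8 ms at one visit. Changes are taken as normal, centred on zero under placebo.

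Expected count at or above 30 ms:

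- placebo: 45 × [1 − Φ(30/σ)]
- active: 45 × [1 − Φ((30 − 8)/σ)]

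95% CI half-width for the between-arm mean difference: t(0.975, 88) × σ × √(2/45) = 1.987 × 0.2108 × σ.

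| σ (ms) | Placebo proportion → count | Active proportion → count | Difference in count | CI half-width (ms) |
|---|---|---|---|---|
| 12 | 0.6% → 0.3 | 3.3% → 1.5 | 1.2 | 5.0 |
| 15 | 2.3% → 1.0 | 7.1% → 3.2 | 2.2 | 6.3 |
| 18 | 4.8% → 2.2 | 11.1% → 5.0 | 2.8 | 7.5 |

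The planned table would thus differ between arms by about one to three subjects. The mean difference would be estimated to within 5.0 to 7.5 ms of an 8 ms effect. With the 80 expected completers (40 per arm), the half-widths grow by about √(45/40) = 1.06, to roughly 5.3 to 8.0 ms.

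**Larger shift, for contrast**

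At 15 ms the active count is 45 × [1 − Φ(15/σ)], which is 4.8, 7.1 and 9.1 for σ = 12, 15 and 18, against 0.3, 1.0 and 2.2 on placebo. The planned table could show a difference of that size.

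**The case against.** Four counter-arguments deserve an answer.

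**Heart rate.** A reader might infer that a heart-rate effect would also be missed. The documents do not support that. SAP 9.3 plans actual values and changes in pulse by visit and arm, vital signs are taken at every ECG visit, and Listing 16.2.8 shows the measurement as heart rate. The objection stands, and heart rate is no part of this point. One detail needs tidying: shell 14.3.4.1 is modelled on 14.3.3.1, which has no change rows, so it should be brought into line with the 9.3 text.

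**QTc change is not ignored.** A reader might conclude that a QTc effect would go unseen. That is too strong. The PCI criteria include a change of 30 msec or more, shell 14.3.5.3 is by visit, and the 15 ms case above would probably show. What remains is that moderate shifts are shown only coarsely.

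**No breach of the protocol wording.** Protocol 13.4.4.3 asks only for appropriate descriptive statistics and names no interval or mean. Protocol 13.4.3, though written for efficacy, treats number and percent as the standard summary of categorical data. So a flat contradiction cannot be claimed. The two-sentence structure, and the treatment of vital signs in that same section, still favour the broader reading.

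**Assumptions and tests.** The SDs and the shift are assumed, and Protocol 13.4.4 plans no formal inference for safety unless otherwise noted. Power figures would also depend on the test chosen. For the 8 ms case, Fisher's exact test on the count gives 0.3% to 8.9% and a chi-square test roughly 5% to 22%, and neither is planned. The illustration therefore rests on expected counts and precision.

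Finally, the listing gap should not be read as a plan to withhold data. SAP 6.2 requires all collected data in listings, the PCI table cannot be programmed without interval values, and Appendix A allows shells to be updated. It is a shell error.

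**Conclusion.** The point holds for PR, QRS, QT and QTc. SAP 9.4 and its shells give no by-visit value or change from baseline for these intervals, unlike laboratory tests and vital signs. On the more natural reading this narrows Protocol 13.4.4.3 without being declared.

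The consequence is loss of information: a moderate mean QTc shift would be poorly shown. Under the assumed SD of 12 to 18 ms and shift of 8 ms, the planned count differs by about one to three subjects per 45, against a CI half-width of 5.0 to 7.5 ms for the mean difference. Those figures illustrate a descriptive comparison and would change with other assumptions. The absence of these summaries does not depend on them.

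This is an inexpensive improvement to a phase 2 safety summary. It does not affect the efficacy conclusions. The listing and source-line errors are minor repairs.

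**What to change.** 1. Add one table to SAP 9.4 and Appendix A, by visit and arm in the Safety Population: value and change from baseline (n, mean, SD, median, minimum, maximum) for PR, QRS, QT, QTcB and QTcF. A 95% CI for the between-arm difference in mean change is optional, since the SAP gives none for other safety variables.
2. State in SAP 9.4 that this table is produced whatever the incidence of abnormal ECGs, so that the sentence "Depending on the incidence of abnormal ECG results, some of these displays might not be needed" cannot be applied to it.
3. Put numeric interval values in the ECG listings (16.2.9/16.2.10), and cite the listing that holds them as the source of Table 14.3.5.3.
4. If the sponsor prefers categorical summaries only, record that in SAP Section 10 as a change from Protocol 13.4.4.3.

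The cost is one table shell, a few listing columns and some lines of SAP text. No new data are collected, because the PCI criteria already need every one of these values.
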